9.2 Analyses Supporting Primary Objective(s)

The primary analysis will focus on quantifying the impact of **Complement Theory on changes in Quality of Life Score (QoLS), measured by the FACT-G instrument**, over the trial period. Assessments will occur at baseline, 3, 6, 9, 12, and 18 months.

- **Statistical Model, Hypothesis, and Method of Analysis**

- Primary Estimand (Change in QoLS):
 - Null Hypothesis (H0): There is no difference in the mean change in FACT-G QoLS between participants in the Complement Theory program and those in the control group at specified time points.
 - Alternative Hypothesis (H1): Participants in the Complement Theory program demonstrate a statistically significant improvement in QoLS compared to the control group.
- Baseline Data Analysis: Baseline demographics and characteristics will be provided and summarized in both treatment and control groups. Standardized mean differences (SMDs) will be calculated as the measure of distance between groups. SMDs of 0.2 to <0.5, 0.5 to <0.8 and ≥0.8 are considered small, medium, and large, respectively. Frequencies and percentage will be provided for the binary variables as well as the categorical variables (Yes/No); mean (standard deviation) and median (range) will be computed for continuous variables.
- Method of Analysis: Mixed models for repeated measures (MMRM) will be utilized to analyze changes in FACT-G scores over time, accounting for within-subject correlations. This model allows for the inclusion of both fixed effects and random effects to account for individual variability. In addition, covariate-time interaction terms will be included to guarantee the best results. The strength of the effect from each covariate will be evaluated

through the statistical test significance, i.e., P value, at 95% confidence interval.

- **Handling of Intercurrent Events of Primary Estimand(s)**

- For participants who discontinue the intervention or are non-adherent, we will employ a treatment policy strategy. This means all data collected will be analyzed as per the initial treatment assignment, regardless of the discontinuation or level of adherence, preserving the intention-to-treat principle.

- **Handling of Missing Data**

- Given the potential for missing QoLS data due to dropout or non-response, a multiple imputation (MI) approach will be adopted. The imputation model will incorporate variables predictive of missingness and outcomes to generate plausible values for missing data.

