- Multivariate imputation by chained equation (MICE) will be used, i.e., filling the missing data multiple times based on the effect from other covariates by constructing a multivariate regression model. MI is superior to single imputation, as it accounts for the uncertainty of missing values in a more robust way. The number of imputations will be 10, i.e., 10 datasets with imputed data will be created. Each imputed dataset gives a point estimate of the regression coefficients as well as its standard deviation, which will be combined across the 10 datasets to obtain the final estimate and their 95% CIs.
- MICE is flexible and can accommodate variables of different types, as well as complexities such as bounded scales or survey skip patterns, making it well-suited for patient-reported outcomes like QoLS.

- **Sensitivity Analysis**

- To complement our intention-to-treat (ITT) analysis, a per-protocol analysis will be performed, including only participants who fully adhered to the intervention, to explore the effect of adherence on QoLS improvement.

- **Supplementary Analysis**

- Efficacy Analysis: survivors in the treatment and control group will be compared for the outcome variables. The comparison will be evaluated based on both SMD and P value. SMD greater than 0.2 will be considered as acceptable differences (section 3.3 indicated the definition of SMD). Descriptive statistics will be compared between treatment groups and control groups, and P values will be calculated using ANOVA tests comparing means of continuous variables, Brown-Mood test to compare the medians, and Chi-Square tests for binary and categorical variables. The differences will be considered as statistically significant within 95% confidence interval, i.e., P value less than 0.05.

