9.7 Sample Size Determination

- The metric-wise sample size calculation is provided in the table below on alpha as 0.05 and power of 80% for the one-tail test at enrollment ratio = 1.
- While we are conducting the power analysis and sample size calculation based on several variables (outcomes) of interest, the sample size was computed separately for each parameter in the study and the greatest is used to obtain sample size.
- The analysis (detailed below in table) showed that sample of size of 102 is powerful enough for the analysis to cover 100% of primary and secondary metrics.
- Now since we believe that the long follow-up duration of 6 months for our trial will lead to around 30% drop-offs, we decided a final sample size of 146 (73 control, 73 test).

- So even if get 30% or 44 participants drop off we end up with final sample set of 102 (51 control, 51 test) and would be able to come to statistically significant effects ($p < 0.05$) with respect to 100% of primary and secondary metrics.

Metric Segment	Sub Metric	Control Data	Test Data	Assumed Variance	Sample Size
Primary Outcome / Concerns					
Quality of Life Improvement	QoLS Score (FACT-G)	70	85	Variance of 20	42 (21 Control, 21 Test)
Secondary Outcome / Concerns					
Presenteeism	Attitude towards work	2	4	Variance of 1.5	16 (8 Control, 8 Test)
	Employee Performance	0.6	0.7	Variance of 20%	102 (51 Control, 51 Test)
Absenteeism	Working Hours	30	40	Variance of 10	28 (14 Control, 14 Test)
	Vacation Days	0.5	0.3	Variance of 0.15	16 (8 Control, 8 Test)
Exploratory Outcomes					
Cancer Care	Cancer Progression Status	0.85	0.88	Variance of 0.04	46 (23 Control, 23 Test)

	Cancer recurrence status	0.3	0.21	Variance of 10%	32 (16 Control, 16 Test)
Medical Expenditure	Total Healthcare Expenditure (Planned + Unplanned)	10000	8000	Variance of 4000	102 (51 Control, 51 Test)
	No of Urgent Care Visits	3	2.5	Variance of 0.5	28 (14 Control, 14 Test)
	No of ED Visits	5	3.45	Variance of 0.8	10 (5 Control, 5 Test)
	No of unplanned outpatient/office visits (other than ED)	4.28	3.5	Variance of 0.8	28 (14 Control, 14 Test)
	Unplanned Hospitalisations	5	4	Variance of 0.8	18 (9 Control, 9 Test)
	Length of hospital stay	3	2	Variance of 0.8	18 (9 Control, 9 Test)
	No of planned outpatient visits	2	1.8	Variance of 0.3	58 (29 Control, 29 Test)
	No of planned hospital visits	1.25	1	Variance of 0.1	10 (5 Control, 5 Test)
	Length of hospital stay	3	2	Variance of 0.8	18 (9 Control, 9 Test)

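### The SMD > 0.2 rule for outcomes in the supplementary efficacy analysis (9.2) either labels chance differences as acceptable or adds nothing to P < 0.05

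*Protocol*

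**What the plan says.** Section 9.2 of the Protocol uses the SMD in two places.

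- **Baseline Data Analysis.** "Standardized mean differences (SMDs) will be calculated as the measure of distance between groups", followed by the scale: "SMDs of 0.2 to <0.5, 0.5 to <0.8 and ≥0.8 are considered small, medium, and large, respectively". This is the only SMD scale in the document.
- **Supplementary Analysis, under the label Efficacy Analysis.** The arms are compared on the outcome variables. "The comparison will be evaluated based on both SMD and P value". Then comes "SMD greater than 0.2 will be considered as acceptable differences", with a pointer to section 3.3 for the definition. P values come from ANOVA (means), the Brown-Mood test (medians) and chi-square (binary or categorical outcomes). The criterion for significance reads: "The differences will be considered as statistically significant within 95% confidence interval, i.e., P value less than 0.05".

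The paragraph does not say whether the SMD and the P value must both be met, in which direction the SMD counts, what an acceptable difference entitles the authors to conclude, or which analysis set is used. Section 3 has one numbered subsection, 3.1, and Section 4 follows it directly, so there is no section 3.3.

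Section 9.2 of the Combined protocol and SAP has the same paragraph with the same cross-reference, although its primary outcome is healthcare expenditure.

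**The concern.** A cut-off that section 9.2 offers as a yardstick for baseline distance, at the bottom of its small range, reappears as a criterion for outcomes under an efficacy label. At this trial's size, 0.2 is about one standard error of an SMD, so it cannot separate an effect from chance.

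What is at stake is reporting. An outcome with an SMD of 0.25 at 51 per arm has a two-sided P of about 0.21, yet it meets the wording for an acceptable difference. Section 1.3 expects publications at 12 and 18 months, and nothing in 9.2 says that the supplementary comparisons cannot support a statement about efficacy.

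**Working it through.** **Inputs.** Section 9.7 gives "alpha as 0.05 and power of 80% for the one-tail test at enrollment ratio = 1", a "final sample set of 102 (51 control, 51 test"), and the expectation that follow-up "will lead to around 30% drop-offs, we decided a final sample size of 146 (73 control, 73 test"). The SMD threshold of 0.2 and the P threshold of 0.05 are from 9.2.

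**Reproducing the plan's sample size.** The Employee Performance row (0.6 against 0.7, with the stated variance of 20% used as a standard deviation of 0.20) gives a standardised effect of 0.1/0.2 = 0.5. A one-sided two-sample t-test at 5% with 80% power needs 50.15, so 51 per arm or 102 in all. Allowing for 30% dropout, 102/0.70 = 145.7, so 146. Both figures match. The two-sided version needs 64 per arm and does not match.

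**Chance of passing the SMD threshold with no true effect.** For n per arm, SE(SMD) = √(2/n), and P(|SMD| > 0.2) = 2 × [1 − Φ(0.2/SE)].

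| | 51 per arm | 73 per arm |
|---|---|---|
| SE(SMD) | √(2/51) = 0.198 | √(2/73) = 0.166 |
| 0.2/SE | 1.01 | 1.21 |
| Either direction, normal | 31.3% | 22.7% |
| Either direction, t distribution | 31.5% | 22.9% |
| Programme's favour only, t | 15.7% | 11.4% |

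A simulation of 200,000 null trials at 51 per arm gave 31.5% in either direction and 15.8% in one direction.

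**Smallest SMD that reaches P < 0.05, for means.** With equal arms, t = SMD/√(2/n), so the critical SMD is t(0.975, 2n − 2) × √(2/n).

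- 51 per arm: 1.984 × 0.198 = 0.393 (one-sided 0.329).
- 73 per arm: 1.977 × 0.1655 = 0.327 (one-sided 0.274).

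All four exceed 0.2. In the same simulation, no trial had P < 0.05 with an absolute SMD of 0.2 or less. Requiring both criteria gave 5.0% false positives, the same as P < 0.05 alone; accepting either gave 31.5%. The critical two-sided SMD falls to 0.2 only at about 194 per arm.

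**Binary outcomes, chi-square test.** The SMD divides |p1 − p2| by the square root of the average within-arm variance. That variance is never larger than the pooled variance used in the chi-square statistic, so P < 0.05 implies an SMD above 1.96 × √(2/n). This is 1.96 × 0.198 = 0.388 at 51 per arm and 1.96 × 0.1655 = 0.324 at 73. A search over all pairs of counts at 51 per arm found a minimum of 0.399.

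**Where redundancy is not shown.** The Brown-Mood test compares medians, so P < 0.05 there does not strictly imply a mean-based SMD above 0.2. For outcomes with more than two categories, the plan does not define an SMD.

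**The case against.** The best defence is that this paragraph decides nothing confirmatory. It is headed as supplementary. In the Protocol, the primary question has its own hypothesis and an MMRM for FACT-G (9.2) on the ITT set (9.1). The secondary outcomes have their own models and hypotheses (9.3). Interim testing uses group sequential methods with an O'Brien-Fleming spending function (9.6). A reader might infer that the trial's efficacy conclusion carries a 31% false-positive rate, but no section lets an SMD replace or override those analyses. This part of the defence stands.

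The wording about both SMD and P value also most naturally means joint consideration, and statistical significance is reserved for P < 0.05. On that reading the SMD rule is mainly redundant, with about a 5% error rate for means. This stands as the likelier reading, but the combination rule is not written down, and the sentence still attaches a favourable word to the SMD alone.

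The 31% counts both directions and uses the number left after dropout. The paragraph names no analysis set; with all 73 per arm, the figure is 23%. For a result in the programme's favour, the range is 11% to 16%. This stands, and both ranges should be shown.

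A reader might also compound the rate over several outcomes as if they were independent. They come from the same participants and the documents give no correlations, so no such figure is supported.

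Finally, a standardised effect size beside a P value is legitimate description. That is true, and SMDs need not be confined to the baseline table. It is the threshold that has no justification.

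**Conclusion.** The concern holds for the supplementary analysis only. The plan borrows a baseline cut-off as an outcome criterion, gives no combination rule or direction, and cites a section that is not there. With no true effect, the SMD passes 0.2 in either direction 23% to 31% of the time, and in the programme's favour 11% to 16%, for 73 and 51 per arm respectively. Used alone, the rule labels noise as a difference. Used with P < 0.05, it changes nothing for tests of means or for binary chi-square comparisons. The stronger claim that it can never matter is not established for the Brown-Mood test. The primary MMRM and the secondary models are untouched.

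The figures assume unadjusted SMDs, equal arms and, for the means, approximately normal outcomes. They depend on n alone. Outcomes limited to employed participants would have fewer per arm, and the documents do not say how many. As an assumed range, 36 per arm would give 40% and 21 per arm 52%, in either direction.

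**What to change.** In section 9.2:

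1. Delete the SMD > 0.2 threshold for outcome variables.
2. If outcome SMDs are reported, give them descriptively with 95% confidence intervals and no cut-off.
3. State that the supplementary SMD, ANOVA, Brown-Mood and chi-square comparisons do not decide efficacy, which rests on the pre-specified primary and secondary models.
4. Replace the section 3.3 reference with a pointer to the Baseline Data Analysis text in 9.2.

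Make the same edit in the Combined protocol and SAP if that document remains in use. The cost is a few sentences of text; data collection, sample size and trial conduct do not change.

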9.3 Analysis Supporting Secondary Objective(s)

- **Secondary Objective 1: Effect on Employee Absenteeism**

- Statistical Model and Hypothesis:
 - Model: Generalized linear models with a Poisson distribution to compare the number of leave days between groups.
 - Hypothesis: H0: No difference in the number of leave days between groups. H1: A significant reduction in leave days in the intervention group.
- Handling of Intercurrent Events:
 - Analysis will consider any change in employment status as an intercurrent event, with a modified intention-to-treat analysis excluding participants who lose their job unrelated to health status.
- Handling of Missing Data:
 - Worst-case scenario imputation for missing absenteeism data, assuming maximum observed absence for missing periods.
- Sensitivity Analysis:

- Repeating analyses with and without worst-case imputation to evaluate the impact of different missing data assumptions on the outcome.
- **Secondary Objective 2: Impact on Employee Presenteeism**
 - Statistical Model and Hypothesis:
 - Model: Mixed-effects models to analyze changes in work motivation and performance review scores over time.
 - Hypothesis: H0: No difference in changes in motivation and performance scores between groups. H1: Significant improvement in these measures in the intervention group.
 - Handling of Intercurrent Events:
 - Job changes or significant alterations in work responsibilities will be documented and explored in sensitivity analyses to understand their impact on presenteeism outcomes.
 - Handling of Missing Data:
 - LOCF for interim missing data points in motivation and performance scores, acknowledging potential limitations in this approach.
 - Sensitivity Analysis:
 - Analysis excluding participants with significant job changes during the trial to assess the effect of such changes on presenteeism outcomes.

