The evaluation of our proposed trial, which integrates live coactive coaching with a software solution for cancer survivors, demonstrates a significant favorable balance between minimal risks and anticipated benefits. The residual risks are minimized through tailored safety measures and are outweighed by the expected benefits of improved physical health, decreased symptom burden, and enhanced quality of life.

Supporting this favorable assessment, a substantial body of research not only confirms the safety of exercise but also endorses the significance of physical activity and lifestyle

changes in cancer management. This evidence base, coupled with medical endorsement of physical activity for enhancing survivor outcomes, bolsters confidence in the trial's approach.

To ensure ongoing safety and integrity, risks and benefits will be continuously assessed, adjusting protocols as necessary to safeguard participant well-being. This trial aligns with best practices in cancer treatment and reflects a commitment to advancing survivor care through evidence-based lifestyle interventions.

Section 3: TRIAL OBJECTIVES, ENDPOINTS AND ESTIMANDS

Trial Objective 1: Impact of Complement Theory's Program on Quality of Life

Clinical Question: How does participation in Complement Theory's program affect Quality of Life Scores (as measured by FACT-G) in cancer survivors compared to those receiving standard care?

- Endpoint(s): Measured through change in FACT-G scores which is designed to assess various dimensions of quality of life including pain levels and sleep quality.
- Estimand(s): The mean difference in change in scores between the intervention and control groups at specified time points during and after the intervention period.

Trial Objective 2: Effect on Employee Absenteeism

Clinical Question: How does participation in the Complement Theory program influence the number of leave days taken by employed cancer survivors due to health issues?

- Endpoint(s): Number of leave days (including sick leave, short-term disability, and long-term disability) taken by participants during the trial period.
- Estimand(s): The difference in the average number of leave days between the intervention and control groups over the trial period.

Trial Objective 3: Impact on Employee Presenteeism

Clinical Question: What is the effect of Complement Theory's program on motivation to work and performance review scores among employed cancer survivors?

- Endpoint(s):

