6.1 Schedule of Events

Schedule of events for test/treatment group:

Intervention or Assessment (Test)	Baseline (Day -30 to -1)	Week	Week	Month 1-6 (Every 30 days)	Month 7-18 (Every 30 days)
		1/3/5/7/9/11/13/15/17/19/21/23/...	2/4/6/8/10/12/14/16/18/20/22/24/...		
Live Coactive Lifestyle Coaching		X	X		

- 3-5 days per week, 45 mins each					
Async access to Lifestyle modification content curated by CT		X	X		
Informed Consent	X				
Eligibility Criteria Assessment	X				
Demographic Details	X				
EHR Access Consent	X				
Claims Data Access	X		X		X
QoLS (FACT-G Form)	X		X		X
Weight	X		X		X
Motivation to work	X	X			X
Employee Performance Review	X	X			X
Absenteeism Questions	X	X			X
Claim data validation with				X	X

survivor						
Cancer Progression Status					X	X

Schedule of events for active comparator (control) group:

Intervention or Assessment (Test)	Baseline (Day -30 to -1)	Week	Week	Month 1-6 (Every 30 days)	Month 7-18 (Every 30 days)
		1/3/5/7/9/11/13/15/17/19/21/23/... /47	2/4/6/8/10/12/14/16/18/20/22/24/... /48		
Async access to publically available lifestyle modification guidance		X	X		
Informed Consent	X				
Eligibility Criteria Assessment	X				
Demographic Details	X				
EHR Access Consent	X		X		X
Claims Data Access	X		X		X
QoLS (FACT-G Form)	X		X		X
Weight	X		X		X
Motivation to work	X	X			X
Employee Performance Review	X	X			X
Absenteeism Questions	X	X			X
Claim data validation with survivor				X	X
Cancer Progression Status				X	X

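### Leave days, disability included, are tested with a plain Poisson model after an undefined worst-case fill, so the error rate is not controlled if counts are overdispersed or forms go missing at the expected rate

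*Protocol*

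**What the plan says.** Protocol Section 3, Trial Objective 2, defines the endpoint as "Number of leave days (including sick leave, short-term disability, and long-term disability) taken by participants during the trial period" and the estimand as "The difference in the average number of leave days between the intervention and control groups over the trial period".

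Protocol 9.3, Secondary Objective 1, sets the analysis:

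- Model: "Generalized linear models with a Poisson distribution to compare the number of leave days between groups".
- Alternative hypothesis: "A significant reduction in leave days in the intervention group".
- Missing data: "Worst-case scenario imputation for missing absenteeism data, assuming maximum observed absence for missing periods".
- Sensitivity: "Repeating analyses with and without worst-case imputation to evaluate the impact of different missing data assumptions on the outcome".

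The Combined protocol and SAP repeats the model, the fill and the rerun in its own 9.3, under Secondary Objective 3. For this endpoint neither document names a dispersion parameter, negative binomial model, robust variance or exposure offset. Neither says whose maximum is meant.

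In Protocol 6.1 the row "Absenteeism Questions" is marked both for odd weeks and for every 30 days in months 7 to 18. The control table runs the odd weeks to week 47.

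**The concern.** A Poisson model sets the variance equal to the mean. Most employed participants may lose a few days, while someone on long-term disability may lose nearly every working day. Pooling the two will usually push the variance above the mean, and the model-based standard error is then too small.

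The fill adds a second source of excess variance. Participants who stop reporting receive large constants and those who keep reporting do not, so the completed totals are a mixture even when the underlying counts are Poisson.

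At stake is one of the Protocol's two secondary objectives. A reduction in leave days could be declared when there is none, with a confidence interval that is too narrow.

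**Working it through.** **Inputs from the documents.** 73 per arm, about 30% dropout, and alpha 0.05 one-tailed with 80% power for sizing (9.7); the endpoint (Section 3); the model and fill (9.3); the form schedule (6.1). **Not in the documents:** the mean and variance of leave days, the number employed, and the sidedness of the 9.3 test. These are assumed below.

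**Step 1. The plan's own figures.** The 9.7 table sizes absenteeism on Working Hours (30 vs 40, spread 10, total 28) and Vacation Days (0.5 vs 0.3, spread 0.15, total 16). A one-sided two-sample t-test that reads the spread as an SD gives 14 and 8 per arm, so 28 and 16, an exact match. Reading the spread as a variance gives totals of 6 and 96. Also 102/(1 − 0.30) = 145.7, so 146. The sizing is therefore a comparison of means on other quantities and supplies no dispersion for leave days.

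**Step 2. Overdispersion alone.** With variance/mean ratio φ, the Poisson z-statistic has standard deviation √φ under the null. The chance of a false reduction is P(Z > 1.645/√φ) for a one-sided 5% test and P(Z > 1.960/√φ) for a two-sided 5% test.

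| φ (assumed) | One-sided (nominal 5%) | Two-sided, false reduction only (nominal 2.5%) |
|---|---|---|
| 1 | 5% | 2.5% |
| 2 | P(Z > 1.163) = 12% | P(Z > 1.386) = 8% |
| 4 | P(Z > 0.822) = 21% | P(Z > 0.980) = 16% |
| 10 | P(Z > 0.520) = 30% | P(Z > 0.620) = 27% |

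Simulated gamma-Poisson trials at 51 and 73 per arm, run at φ of 1, 2, 3, 5 and 10, agree with the formula within about 1 point.

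**Step 3. The fill alone, on exactly Poisson counts.** Assumed: 18 monthly periods, 0.5 days/month, 73 per arm, 30% dropout in both arms. One-sided null error is about 33% with the cohort maximum, 21% with the participant's own maximum and 5% with complete cases. A second assumed layout (6 periods, mean 1 day each) gives 23% (cohort), 28% (arm) and 10% (own). There the fill raises φ from 1 to 5.3, 4.6 and 1.8. The choice of maximum matters as much as the data.

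**Step 4. Unequal dropout.** Take 25% dropout in test and 35% in control, no disability cases and no true effect. Over assumed rates of 0.2 to 1.0 days/month, with and without between-person variation, the rate ratio averages 0.77–0.94 (cohort), 0.79–0.94 (arm) and 0.90–0.99 (own). Complete cases give 0.99–1.01. With the dropout reversed, the ratios are 1.07–1.32, 1.06–1.30 and 1.01–1.12. The arm that loses more people looks worse.

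**Step 5. The rerun without the fill.** It changes the missing-data rule and leaves the variance at Poisson. Its simulated one-sided error is 13–14% at φ about 2.2, 19–23% at 4–5 and 27–31% at 7–10.

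**Step 6. The schedule.** Week 47 ends on day 7 × 47 = 329. Month 7 starts on day 6 × 30 + 1 = 181, and 329/30 = 10.97. Two-weekly and 30-day forms therefore both apply in months 7 to about 11. The Combined document stops the odd weeks at 23 and has no such overlap. Until this is settled, the period that a maximum refers to is undefined, and days could be counted twice.

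**The case against.** **Dispersion is not shown to exceed 1.** This stands as a limit. A reader might infer that the Poisson test always exceeds 5%; the documents do not support that. Per unit, the Vacation Days row gives a ratio of 0.15/0.5 = 0.3 to 0.15/0.3 = 0.5, or 0.15²/0.5 = 0.045 to 0.15²/0.3 = 0.075 if 0.15 is an SD. At such values Poisson is conservative. But that row is a different quantity with no time unit and no disability in it, so it neither proves nor rebuts overdispersion of leave days. Step 3 does not need it.

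**Sidedness.** It is tempting to quote only the one-sided rates, because 9.7 sizes one-tailed and the hypothesis is directional. Yet 9.3 does not state sidedness, and 9.2 uses 95% intervals and P below 0.05. Both columns are needed.

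**Comparisons of means are already planned.** Section 8.2 compares average leave days, and the supplementary analysis in 9.2 lists ANOVA for outcome variables. ANOVA on unimputed leave days held 4–6% two-sided in simulation. However, 9.2 supports the primary objective, and 9.3 names the Poisson model as the test for this endpoint.

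**The rerun is a safeguard.** It does expose sensitivity to the fill, but it does not correct the standard errors. A reader might also expect it to be biased the opposite way. That holds only if observed days are summed without an offset, not for complete cases.

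**An analyst could add a scale parameter.** Nothing forbids this, but nothing written requires it, and the choice would then come after the data are seen.

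**Conclusion.** The concern holds, and 9.3 is wrong as written on this endpoint rather than merely short of detail: following it literally gives standard errors that are too small in plausible conditions. The direction is certain once φ exceeds 1. The size is not fixed by the documents, and every rate above depends on an assumed φ, leave rate or period layout. The fill inflates error at equal 30% dropout even when the counts are exactly Poisson, and under unequal dropout it also biases the estimate against the arm that loses more people. If the test arm loses more, that bias works against the intervention, so it would be wrong to say that the fill always favours the programme.

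A reader might extend this to the trial's main conclusion. The documents do not support that, because the FACT-G analysis in Protocol 9.2 uses a different model and a different missing-data method.

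**What to change.** In 9.3, with the matching change in the Combined document if it remains in force:

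1. **Main analysis.** Use a log-rate model on observed reporting periods, with an offset for observed time, period (calendar-interval) effects and cancer type, and a robust (sandwich) or quasi-Poisson variance. Report the difference in mean leave days with its confidence interval, to match the Section 3 estimand. In gamma-Poisson simulations at φ of 2, 5 and 10, one-sided error was 5.1–5.3% with quasi-Poisson and 5.3–5.6% with sandwich variance. The period effects matter: when leave falls steeply over time and dropout is 25% test/35% control, an offset model without them gave 11–14%, and adding them brought it back to about 5–6%. Re-randomisation within cancer type is an optional check.
2. **Sidedness.** State whether the test is one- or two-sided.
3. **Worst-case fill.** Keep it as a sensitivity analysis only, using the cohort's or the participant's own maximum for a period of the same length, with the same variance method. Do not use the arm's maximum: with robust variance and equal dropout it still gave 6.7–24.5% one-sided error.
4. **Schedule.** Reconcile the overlapping absenteeism columns in 6.1 so that each period is counted once.

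**Cost.** SAP wording and standard software. The interval widens by about √φ: 1.4, 2 and 3.2 times at φ = 2, 4 and 10. The detectable reduction, as a fraction of the mean μ, is (1.645 + 0.842) × √(2φ/(nμ)). With an assumed μ of 9 days, one-sided 5% and 80% power (for example n = 73, φ = 4: 2.487 × √(8/657) = 27%):

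| Per arm | φ = 2 | φ = 4 | φ = 10 |
|---|---|---|---|
| 73 | 19% | 27% | 43% |
| 51 | 23% | 33% | 52% |
| 30 employed (assumed) | 30% | 43% | 68% |

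The observed-period analysis assumes that missing reports are unrelated to leave, given the period. The retained worst-case run probes that assumption, but under unequal dropout it stays biased even with a robust variance.
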